Background: Syrian refugees face multiple hardships and adversities, which puts them at risk for the development of mental health problems. However, access to adequate mental health care in host countries is limited. The WHO has developed Problem Management Plus (PM+), a brief, scalable psychological intervention, delivered by non-specialist helpers, that addresses common mental disorders in people affected by adversity. This study is part of the larger STRENGTHS project, that aims to evaluate peer-refugee delivered psychological interventions adapted for Syrian refugees in Europe and the Middle East.

Objective: To evaluate the effectiveness and cost-effectiveness of the adapted peer-refugee delivered PM+ intervention among Syrian refugees with elevated levels of psychological distress in the Netherlands.

Methods: The adapted PM+ intervention will be tested in a randomized controlled trial (RCT) among Arabic-speaking Syrian refugees in the Netherlands aged 18 years and above with self-reported psychological distress (Kessler Psychological Distress Scale; K10>15) and impaired daily functioning (WHO Disability Assessment Schedule; WHODAS 2.0 >16). Participants ($N=380$) will be randomized into care as usual with PM+ (CAU/PM+, $n=190$) or CAU only (CAU, $n=190$). Baseline, 1-week post-intervention, 3-month and 12-month follow-up assessments will be conducted using tablet-assisted self-interviewing software with audio support. Primary outcomes are symptoms of depression and anxiety. Secondary outcomes are functional impairment, posttraumatic stress disorder symptoms, self-identified problems, anger, health and productivity costs, and hair cortisol concentrations. A process evaluation will be carried out to evaluate stakeholder views on barriers and facilitators to implementing PM+, as well as treatment dose and protocol fidelity.

Discussion: PM+ has proved effectiveness in other populations and settings. After positive evaluation of the PM+ intervention with Syrian refugees, the adapted manual and training

materials for individual PM+ will be made available through the WHO to encourage further replication and scaling up.

Trial registration: Trial registration Dutch Trial Registry, NL7552, registered prospectively on March 1, 2019. Medical Ethics Review Committee VU Medical Center Protocol ID 2017.320, 7 September 2017).

Key-words: Refugee mental health, Randomized controlled trial, Psychological intervention, Task-shifting, Non-specialist counsellors, Common mental disorders, Depression, Anxiety, Posttraumatic stress disorder, Hair cortisol

Background

Since the outbreak of the Syrian civil war in 2011 over 12 million Syrians have been displaced. In the Netherlands, 31.500 Syrian refugees have been registered (UNHCR, 2019).

The war in Syria has led to an excessive number of civilian casualties (Devi, 2018). High rates of war-related trauma have been reported, with the majority of Syrian refugees having experienced at least three traumatic events during or after their migration (Ibrahim & Hassan, 2017). Seeking refuge in Europe is a risky and stressful journey (Ben Farhat et al., 2018). Once arrived in Europe, refugees may face uncertainty about their asylum applications, problems with integration, loss of social networks and social status, discrimination, worries about family in Syria, and restricted economic opportunities (Kirmayer et al., 2011; Laban, Gernaat, Komproe, Van Der Tweel, & De Jong, 2005).

Refugees are at increased risk to develop depression, anxiety, posttraumatic stress disorder (PTSD) and related somatic health symptoms (Silove, Ventevogel, & Rees, 2017). A recent study among Syrian refugees in the Netherlands found that 41% report psychological distress (Dagevos, Huijnk, Maliepaard, & Miltenburg, 2018). Studies among Syrian refugees in camp and non-camp settings in Europe report prevalence rates ranging from 14.5-44% for depression (Georgiadou, Zbidat, Schmitt, & Erim, 2018; Poole, Hedt-Gauthier, Liao, Raymond, & Bärnighausen, 2018), 13.5-92% for anxiety (Ben Farhat et al., 2018; Georgiadou et al., 2018) and 11.4-83.4% for PTSD (Acarturk et al., 2018; Georgiadou et al., 2018).

Studies have shown that trauma exposure and symptoms of PTSD (Schumacher et al., 2019; Stalder et al., 2017) and depression (Knorr, Vinberg, Kessing, & Wetterslev, 2010) are associated with altered hypothalamic-pituitary-adrenal (HPA) axis function, suggesting HPA hyperactivity in depression (Knorr et al., 2010) and both hypo- (Schumacher et al., 2019) and hyperactivity in PTSD (Stalder et al., 2017), although some meta-analyses found no relationship (Klaassens, Giltay, Cuijpers, van Veen, & Zitman, 2012; Meewisse, Reitsma, de

Vries, Gersons, & Olf, 2007). Inconsistencies across findings have been explained by the use of different time points or methods of cortisol assessment across studies, or factors such as type of trauma (ongoing versus single trauma) (see Fragkaki, Thomaes, & Sijbrandij, 2016).

In the past decade, researchers have started to examine hair cortisol concentrations (HCC), which is an economical, non-invasive and reliable method to capture long-term cortisol levels (Stedte-Schmiedgen, Kirschbaum, Alexander, & Stalder, 2016). HCC was found to be lower in trauma-exposed individuals and individuals with PTSD than in non-trauma exposed individuals (Stedte et al., 2013). Factors such as time since trauma-exposure, and number and severity of traumatic events seem to differentially influence HCC (Stedte-Schmiedgen et al., 2016). A recent meta-analysis showed that HCC was higher in trauma-exposed populations with recent or ongoing stress than in trauma-exposed populations with past or absent stress (Stalder et al., 2017; Stedte-Schmiedgen et al., 2016).

Interestingly, a recent study in war-affected adolescents suggested that a brief psychosocial intervention decreased HCC for adolescents with cortisol hypersecretion, whereas it increased HCC in adolescents with hyposcretion relative to controls (Dajani, Hadfield, van Uum, Greff, & Panter-Brick, 2018). Psychological interventions targeting the reduction of daily stress may thus have the potential to normalize cortisol levels, particularly in populations exposed to high levels of ongoing stress, such as refugees. Although these results are promising, the effects of psychological interventions on the reduction of HCC deserve further study.

Despite the availability of specialized mental health services, there are numerous barriers to the delivery and uptake of psychological interventions for refugees (WHO, 2015). These include communication difficulties such as language barriers and interpreter costs (Satinsky, Fuhr, Woodward, Sondorp, & Roberts, 2019), stigma around mental illness (Hassan, Ventevogel, Jefee-Bahloul, Barkil-Oteo, & Kirmayer, 2016), waitlists (Satinsky et

al., 2019), and difficulties navigating within a foreign health care system (Dorn et al., 2011). Treatment programs usually focus on single psychiatric disorders (such as PTSD), whereas many refugees suffer from multiple psychological problems (Thabet, Abed, & Vostanis, 2004). Furthermore, culturally adapted psychological interventions may be more effective compared with interventions to which no (cultural) adaptations have been made (Harper Shehadeh, Heim, Chowdhary, Maercker, & Albanese, 2016). However, there is a lack of mental health interventions adapted for people from Syria.

The WHO has developed the scalable Problem Management Plus (PM+) intervention, which is part of a new generation of short, less expensive and trans-diagnostic (i.e., not condition-specific) interventions to reduce common mental health symptoms and improve psychosocial functioning. PM+ is based on the WHO treatment guidelines for conditions related to stress (WHO, 2013) and includes empirically supported cognitive behavioral therapy strategies, such as stress management, problem solving, behavioral activation and strengthening social support. The intervention covers five weekly face-to-face sessions of 90 minutes with a non-specialist helper. PM+ has been positively evaluated in two randomized controlled trials (RCTs) with 421 female victims of gender-based violence in Nairobi, Kenya (Bryant et al., 2017) and 346 primary care patients in Peshawar, a conflict-affected rural area in Pakistan (Rahman et al., 2016). Participants in the PM+ group had better outcomes on psychological distress, PTSD and daily functioning compared to participants in the enhanced usual care group (Bryant et al., 2017; Rahman et al., 2016). A group version of PM+ was effective in reducing psychological distress and improve functioning in females in Swat, Pakistan (Rahman et al., 2019).

The aim of the current study is to evaluate the effectiveness and cost-effectiveness of the adapted version of individual PM+ for Syrian refugees in the Netherlands impaired by elevated levels of psychological distress on symptoms of depression and anxiety. In addition,

we will assess the effect of PM+ on functional impairment, symptoms of PTSD, self-identified problems, anger, health and productivity costs, and HCC. Furthermore, we will examine the processes of implementation, mechanisms of impact, and contextual influences through a process evaluation.

Methods

Design

This study is part of the EU Horizon2020 STRENGTHS project that aims to evaluate scalable psychological interventions for Syrian refugees in a series of trials in eight countries in Europe and the Middle East (see Sijbrandij et al., 2017). In the Netherlands, we will conduct a single-blind RCT comparing care as usual with PM+ (CAU/PM+) to CAU alone in 380 study participants. A flowchart of the study design is shown in Figure 1. A process evaluation will be conducted to examine barriers and facilitators to implementing PM+, and PM+ dose and protocol fidelity.

[Insert Figure 1 here]

Participants

We will include adult (18 years and above) Syrian refugees who are Arabic-speaking and report elevated levels of psychological distress and impaired daily functioning, as indicated by a score of >15 on the Kessler Psychological Distress Scale (K10) (Kessler et al., 2002) and a score of >16 on the WHO Disability Assessment Schedule 2.0 (WHODAS 2.0) (WHO, 2010). Information about the cut-off values is presented under ‘screening measures’.

Exclusion criteria include acute medical conditions, imminent suicide risk or expressed acute needs or protection risks (e.g., a woman who expresses that she is at acute risk of being

assaulted), severe mental disorders (e.g., psychotic disorders, substance-dependence), cognitive impairment (e.g., severe intellectual disability or dementia), and receipt of current specialized psychological treatment.

Procedure

The PM+ intervention will be implemented within i-Psy (Parnassia Groep), a country-wide transcultural mental health care institution. Participants will be recruited from the community (i.e., Syrian refugees with a residence permit), as well as from reception centres (i.e., Syrian refugees awaiting their asylum request) through i-Psy, (non-governmental) organizations, and social media.

Written informed consent (IC) will be asked from all participants, or witnessed oral informed consent from illiterate participants. The witness will be any adult person (not related to the participant and not part of the research team) who the participant is comfortable having present during consent, and who is willing to act (and sign) as the witness. The project has been approved by the Research Ethics Review Committee of the VU Medical Center, the Netherlands (Protocol ID: NL61361.029.17, September 7, 2017).

After IC is obtained, participants will be asked to complete the two self-report measures on psychological distress (K10) and daily functioning (WHODAS 2.0). Participants who meet the inclusion criteria will be assessed for suicidal ideation (PM+ manual suicidal thoughts interview) and severe disorders (PM+ manual observation checklist). The independent assessors will refer individuals meeting any of the exclusion criteria to specialist support according to their needs.

Participants who meet all inclusion criteria will complete the baseline assessment at the same visit. This involves questionnaires on depression and anxiety (25-item Hopkins Symptoms Checklist; HSCL-25), trauma exposure (Trauma Experiences checklist), daily

stressors (Post-Migration Living Difficulties; PMLD), posttraumatic stress (PTSD Checklist for DSM-5; PCL-5), self-identified problems (Psychological Outcomes Profiles; PSYCHLOPS), anger (Trait Anger Scale; STAS-T), and questions on access to health services. Furthermore, the assessor will administer a health service utilisation and productivity impact interview (locally adapted version of the Client Service Receipt Inventory; CSRI).

The post-assessment (WHODAS 2.0, HSCL-25, PMLD, PCL-5, PSYCHLOPS, CSRI) is scheduled 6 weeks after the baseline assessment (or 1 week after the 5th PM+ session). The follow-up assessments are scheduled 3 months after the 5th PM+ session (WHODAS 2.0, HSCL-25, PMLD, PCL-5, PSYCHLOPS, STAS-T, CSRI) and 12 months after baseline (all 3-month follow-up measures and the Traumatic Experiences checklist, except the STAS-T). We also measure hair cortisol concentrations (HCC) at baseline and 3-month follow-up to investigate the effect of PM+ on HCC.

All questionnaires, except the exclusion instruments (the PM+ manual's suicidal thoughts interview and assessment tool for severe disorders) and the CSRI interview are self-administered on a tablet with audio functions (cf. Morina et al., 2017). Independent Arabic-speaking assessors with at least a degree-level will carry out the assessments. Assessors will receive a three-day training on the administration of questionnaires, use of the tablets, general interview techniques, common mental disorders, psychological first aid and ethical research conduct. The assessors are blinded to treatment allocation.

Sample size

Power calculations were carried out by the VUmc Department of Epidemiology and Biostatistics. Based on previous RCTs on PM+ (Bryant et al., 2017; Rahman et al., 2016), we aim for a conservatively estimated small to medium Cohen's *d* effect size of 0.4 in the PM+ group at 3-months follow-up. Power calculations suggest a minimum sample size of 133

participants per group (power = 0.90, α = 0.05, two-sided). Taking into account an expected 30% attrition rate at the 3-month follow-up, we aim to include a total number of 380 participants (190 in the CAU/PM+ group and 190 in the CAU group).

Randomization

After baseline, participants will be randomized into the CAU/PM+ group or CAU group. Permuted blocks randomization will be performed using computerized software on a 1:1 basis and by means of sealed opaque envelopes. Household members will be randomized together to decrease the risk of contamination. The first PM+ session will be scheduled within one week after the baseline assessment.

Problem Management Plus (PM+)

We will test individual PM+ delivered by Syrian peer-refugees. During this 5-week intervention, a new treatment strategy is introduced in every session and subsequently reviewed in all following sessions. Stress management is practiced in session 1 using a slow breathing exercise. Problem management is taught in session 2 using a step-by-step plan to pro-actively manage practical problems. Behavioral activation is introduced in session 3 by encouraging the participant to re-engage with pleasant and task-oriented activities. Strategies to strengthen social support are discussed in session 4. Homework assignments are carried out between the sessions and relapse prevention strategies are discussed in session five (Dawson et al., 2015; Sijbrandij et al., 2017).

The adaptation of the PM+ intervention and development of training materials was coordinated by the Danish Red Cross in collaboration with the WHO and partners in STRENGTHS. Adaptations were made according to a framework for the cultural adaptation of psychological interventions (Bernal & Sáez-Santiago, 2006), and involved a literal

translation by an Arabic-speaking translator, qualitative interviews with stakeholders such as Syrian refugees and mental health professionals (cf. Applied Mental Health Research Group, 2013), and cognitive testing of the literally translated manual. The core components of the PM+ intervention (e.g., breathing exercise) were retained, while case examples were rephrased to fit the context of Syrian refugees.

PM+ will be delivered by Arabic-speaking male and female refugees from Syria who have completed high school, have a background in education, social work, health care or another related field, and with sufficient speaking ability in Dutch or English. They will receive eight days of training, followed by two practice cases, and close supervision by trained PM+ trainers and supervisors throughout the trial. The training of helpers (ToH) involves education about common mental disorders, basic counselling skills, delivery of intervention strategies and self-care (Rahman et al., 2016).

PM+ trainers and supervisors will be licensed mental health care professionals. They will be trained in a five-day training-of-trainers (ToT) program. The ToT covers the elements of the ToH as well as training and supervision skills (Rahman et al., 2016). Face-to-face supervision of helpers will take place on a weekly basis. The supervisors themselves will be supervised fortnightly by the master trainer who provided the ToT. This training model has previously been successfully implemented (Dawson et al., 2015).

Care as usual

Care as usual (CAU) includes all (mental) health services available to refugees in the Netherlands. Health care for asylum seekers is organized and financed on a national level by the Central Agency for the Reception of Asylum Seekers (COA). Health care, including mental health care for adults is provided by a COA-contracted insurer, and public health care is provided by Community Health Services, Regional Medical Emergency Preparedness and

Planning (GGD-GHOR) and the Centre for Youth and Family (CJZ). Resettled Syrian refugees with a residence permit have to pay a basic health insurance, and have access to health services through their local general practitioner (Fuhr et al., In Press; Kroneman et al., 2016).

Screening measures

An overview of all study measures is provided in Table 1. The WHODAS 2.0 is a generic instrument to assess health and disability and is used across all diseases, including mental, neurological and substance use disorders. It is easy to administer, applicable across cultures and can be used in all adult populations. The cross-culturally validated 12-item version covers difficulties that people experience due to their illness across six domains during the last 30 days (WHO, 2010). Difficulties are scored on a five-point Likert scale ranging from 1 (none) to 5 (extreme), before summation (range 12-60). In line with the earlier RCTs on PM+ a cut-off of >16 will be used (Bryant et al., 2017; Rahman et al., 2016). The WHODAS will also be administered as secondary outcome measure.

The K10 will be used to measure psychological distress. Ten items related to depression and anxiety are rated on a five-point Likert scale, before summation (range 10-50). The K10 has been validated in Arabic-speaking populations (Fassaert et al., 2009; Sulaiman-Hill & Thompson, 2010). In a study among Kurdish and Afghan (former) refugees and asylum seekers in New Zealand and Australia the following cut-off scores were used: 10-15.9 (low risk of psychological distress), 16-21.9 (moderate levels of distress consistent with a diagnosis of moderate depression and/or anxiety disorder), 22-29.9 (high level of distress) and 30 or more (possibility of very high or severe levels of distress) (Sulaiman-Hill & Thompson, 2010). In the current study, we will use a score of >15 as an indication of moderate to high levels of psychological distress.

Sociodemographic information (sex, age, education, work, marital status and time elapsed since displacement) will be collected through items based on the demographic section of the WHODAS 2.0.

[Insert Table 1 here]

Primary outcomes

The primary outcomes are the level of depression and anxiety 3 months after the post-assessment (or fifth PM+ session), as measured by the HSCL-25. The HSCL-25 is a self-report questionnaire for symptoms of psychological distress (Derogatis, Lipman, Rickels, Uhlenhuth, & Covi, 1974). Items are rated on a four-point (1-4) Likert scale. Item mean scores can be calculated for the depression (15 items) and anxiety subscales (10 items). The HSCL-25 has been used with Syrian refugees (e.g., Acarturk et al., 2016).

Secondary outcomes

Posttraumatic stress symptoms during the past week will be measured through the 20-item PTSD Checklist for DSM-5 (PCL-5) (Blevins, Weathers, Davis, Witte, & Domino, 2015). Items are rated on a 0-4 scale and add up to a total severity score of 80, with higher scores indicating worse symptomatology. The PCL-5 has been validated in war-affected adults from Syria and Iraq (Ibrahim, Ertl, Catani, Ismail, & Neuner, 2018).

Self-identified problems will be measured using the PSYCHLOPS, a patient-generated outcome measure as an indicator of change after therapy (Ashworth et al., 2004). The questionnaire consists of four questions covering three domains: problems (2 questions), function, and wellbeing. Participants are asked to give free text responses to the problem and function domains, and these responses are scored on a 0-5 scale (range 0-20). The

PSYCHLOPS has been used in primary care populations across several countries (Czachowski, Seed, Schofield, & Ashworth, 2011; Rahman et al., 2016).

Trait anger will be measured using a modified version of the 10 trait anger items of the State-Trait Anger Scale (STAS-T) (Spielberger, Jacobs, Russell, & Crane, 1983). Scores range from 1 (almost never) to 4 (almost always; total range 10-40).

Health service utilization, receipt of informal family care and impacts on participation in employment (where entitled to work) will be measured through an adapted version of the CSRI. Appropriate unit costs for service contacts will be attached to calculate changes in health service utilisation and health care costs, while minimum wage rates will be used to conservatively value changes in informal care and work-related productivity. We adapted the original CSRI (Beecham & Knapp, 1992) for use in Syrian refugees in the Netherlands. Given that study participants may be unfamiliar with the Dutch health care system, we decided to administer this questionnaire as an interview.

HCC will be measured through hair samples of ~100 strands of hair, collected as close as possible to the scalp at the vertex posterior. Scalp-near 3-cm hair segments, allowing for the examination of cumulative cortisol levels over a 3-month period will be analyzed to determine cortisol content at baseline and 3-month follow-up.

Other measures

Trauma exposure will be measured using a self-constructed 27-item list recoding traumatic experiences. It includes items from the Harvard Trauma Questionnaire (HTQ) (Shoeb, Weinstein, & Mollica, 2007), and the Posttraumatic Diagnostic Scale (PDS) (Foa, Cashman, Jaycox, & Perry, 1997), and has been adapted to include specific traumatic experiences of Syrian refugees experienced before, during or after the flight. Items are scored as 1 (yes) or 0 (no), with a total range of 0-27.

Post-migration stressors will be assessed using the Post-Migration Living Difficulties checklist (PMLD) (Silove, Sinnerbrink, Field, Manicavasagar, & Steel, 1997). This 17-item scale examines the extent to which post-migration challenges have been of concern to the individual over the past 12 months. Items are rated on a five-point scale, ranging from 0 (not a problem) to 4 (a very serious problem). Items scored at least 2 (a moderately serious problem) are considered positive responses, yielding a total count of living difficulties (range 0-17). This scale has previously been used in Arabic speaking refugees (Schick et al., 2016).

Access to health services will be assessed using a self-constructed survey.

Translation and adaptation of the measures

Validated Arabic-language measures were selected when available. Measures were pilot-tested through cognitive interviews with Arabic-speaking Syrians. Instruments without Arabic translation were translated and back-translated. Discrepancies in translation were discussed item-by-item and resolved through consensus between the translators. These steps are in line with the WHO-guidelines on the translation and adaptation of research instruments (WHO, 2018).

Process evaluation

The mechanisms, challenges and successes of the intervention will be explored through semi-structured interviews with key informants, including PM+ participants, helpers, policy makers and health professionals, until saturation is reached. We will use purposive sampling to select a diverse range of respondents. IC will be obtained from all participants, including consent to audio record the interview. An interview will last between 30-60 minutes.

Additionally, PM+ dose (i.e., number of sessions completed), and treatment fidelity and quality will be assessed. All PM+ participants will be asked for IC to audio record the PM+

sessions for protocol adherence purposes. A random sample of 10% of the audio recordings will be coded by an independent researcher with in-depth knowledge of PM+. Helpers will complete fidelity checklists addressing the PM+ components during the sessions (cf. Bryant et al., 2017; Rahman et al., 2016).

Trial monitoring and adverse events reporting

The VU research team has full access to the trial dataset. Adverse events (AE) or serious adverse events (SAE) are defined as any undesirable experience occurring to a participant during the study, whether or not considered related to the trial procedure or the PM+ intervention. All SAEs will be recorded in Castor EDC trial monitoring software (Ciwit BV, 2018) and reported to the SB and to the Central Committee on Research Involving Human Subjects within 7 days (in case of death or life-threatening situation) or 15 days (all other SAEs) after being informed about the event. SAEs will be followed-up until they have abated or until a stable situation has been reached, and if necessary, referral to a general physician will be made.

Analysis

To measure comparisons at baseline between the two treatment groups, t-test (continuous variables) or chi-square tests (categorical variables) will be conducted for normally distributed data; Mann-Whitney tests will be conducted for continuous non-normally distributed data.

Both intention-to-treat (ITT) analysis, including all randomized participants ($N=380$), and completers' analysis will be carried out. The main conclusion will be based on the ITT analysis. To estimate the treatment effect, a linear mixed model will be employed for the primary endpoint analysis, which will have treatment as fixed effects, baseline measurement of primary endpoint as covariate, and subject as random effects. The mean difference between

the two arms at each assessment with its 95% confidence interval will be derived from the mixed model. The effects of PM+ on secondary outcomes (i.e., functional impairment, symptoms of PTSD, self-identified problems, anger, health and productivity costs, and HCC) will be examined using linear mixed models with treatment as fixed effects, baseline measurement as covariate, and subject as random effects. Covariate-adjusted mixed model of primary endpoint will also be performed by adding relevant covariates at baseline (e.g., gender, age, education, baseline levels of depression, anxiety, PTSD, traumatic experiences, post-migration living difficulties, and HCC hypo- versus hypersecretion, etc.) to the above-mentioned model.

For the economic analysis incremental cost-effectiveness ratios (ICERs) will be generated comparing changes in mean costs and primary outcomes from a payer and societal perspective between the two arms. Non-parametric bootstrapping analyses to derive 95% confidence intervals around ICERs , and cost-effectiveness acceptability curves will be generated showing the likelihood that PM+ would be cost-effective at different willingness-to-pay thresholds.

Descriptive analyses will be carried out in SPSS and hierarchical linear modeling analyses in R version 3.6.0. Across all analyses, two-tailed tests will be reported with $p < 0.05$.

Interview transcripts from the process evaluation will be analyzed thematically following the framework approach (Pope, Ziebland, Mays, & Mays, 2000) using NVivo version 11 (QSR International Pty Ltd, 2015).

Discussion

In this RCT we aim to evaluate the effectiveness and cost-effectiveness of the peer-refugee delivered PM+ intervention among Syrian refugees in the Netherlands impaired by symptoms

of psychological distress. Within the larger STRENGTHS project, other RCTs with different modes of delivery (see Sijbrandij et al., 2017) will be conducted among Syrian refugees in Europe and the Middle East, which will strengthen external validity of trial findings and provide a potential model for scaling up in both high- and low-income settings.

Prior research to PM+ has shown that brief interventions delivered by non-specialist helpers are effective in decreasing symptoms of psychological distress, including depression, anxiety and PTSD (Bryant et al., 2017; Rahman et al., 2016, 2019). To our knowledge, this is one of the first RCTs to evaluate brief, non-specialist helper-delivered psychological interventions for refugees in high-income countries and provides a unique opportunity for global lessons on the mechanisms of identifying, recruiting, training and supervising peer-refugee helpers.

The Netherlands is a high-income setting where specialized mental health interventions are available to refugees and migrants, but access is limited due to various barriers (Lamkaddem et al., 2014; Satinsky et al., 2019). By offering PM+ we hope to contribute to overcoming barriers to accessing care, thereby reducing the treatment gap for Syrian refugees in the Netherlands. After positive evaluation of the adapted PM+ intervention, the manual and training materials will be made available through the WHO to encourage scaling up.

Funding

The study is funded by the European Union's Horizon 2020 Research and Innovation intervention Societal Challenges under Grant Agreement No 733337.

Disclosure statement

The authors declare that they have no competing interests.

References

<https://doi.org/10.1097/NMD.0000000000000693>
<https://doi.org/10.1017/S0033291716001070>
- Applied Mental Health Research Group. (2013). *Design, implementation, monitoring, and evaluation of mental health and psychosocial assistance programs for trauma survivors in low resource countries: A user's manual for researchers and program implementers*. Baltimore, MD: John Hopkins University Bloomberg School of Public Health.

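### The primary 3-month assessment is tied to the fifth PM+ session, which the control arm does not have, and two sections of the protocol give different anchors for it

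*Protocol*

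**What the plan says.** The Procedure section of the protocol gives the post-assessment two anchors: it "is scheduled 6 weeks after the baseline assessment (or 1 week after the 5th PM+ session"). For the 3-month visit it names only one: "The follow-up assessments are scheduled 3 months after the 5th PM+ session". The 12-month visit, by contrast, is counted from baseline for everyone.

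The Primary outcomes section defines the endpoint on which the trial will be judged: "The primary outcomes are the level of depression and anxiety 3 months after the post-assessment (or fifth PM+ session), as measured by the HSCL-25". By the Procedure section's own schedule, those two events are a week apart.

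The Design section describes the trial as "comparing care as usual with PM+ (CAU/PM+) to CAU alone in 380 study participants", so the control arm has no PM+ sessions. The Analysis section bases the main conclusion on all randomized participants. The Process evaluation section records how many sessions each participant completed, so incomplete attendance is foreseen. The text gives no timing rule for a PM+ participant who never reaches session 5.

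**The concern.** When follow-up is counted from a treatment session, the calendar time of the primary measurement in the PM+ arm depends on how treatment was delivered after randomization. The control arm has no equivalent. If symptoms drift over time regardless of treatment, any difference between the arms in time since randomization enters the treatment contrast. Its sign and size are then set by session scheduling, not by the effect of PM+. In addition, a scheduler who follows the Procedure section and one who follows the Primary outcomes section would book the same participant a week apart.

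**Working it through.** **The plan's own figure.** The sample size is not affected by this point. With d = 0.4, two-sided alpha 0.05 and power 0.90, a two-sample t-test needs 132.3 per group, rounded up to the stated 133. Allowing for 30% attrition, 133 / 0.70 = 190 per group, or 380 in total. Both figures reproduce.

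**Inputs from the protocol**
- Start of PM+ (Randomization): "The first PM+ session will be scheduled within one week after the baseline assessment".
- Spacing (Background): "The intervention covers five weekly face-to-face sessions of 90 minutes with a non-specialist helper".
- Post-assessment (Procedure): week 6 from baseline, or session 5 plus 1 week.
- 3-month visit: session 5 plus 3 months (Procedure), or post-assessment or session 5 plus 3 months (Primary outcomes).

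**Assumptions not in the protocol**
- 3 months is taken as 13 weeks.
- An illustrative total slip in sessions of 3 weeks.
- Natural improvement of 0.01-0.03 SD per week.

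**CAU timing.** Only the baseline-based anchor can apply: 6 + 13 = week 19.

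**PM+ timing.** Session 5 = session 1 (week 0-1) + 4 weekly intervals + slip.

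| Delivery | Session 5 | Session 5 + 13 | (Session 5 + 1) + 13 | Gap to CAU at week 19 |
|---|---|---|---|---|
| On time | week 4-5 | week 17-18 | week 18-19 | 2 to 0 weeks earlier |
| 3-week slip | week 7-8 | week 20-21 | week 21-22 | 1 to 3 weeks later |

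If a PM+ participant's post-assessment is instead held at week 6 regardless of sessions, and the 3-month visit is counted from it, the visit falls at week 19 and the gap is zero. The wording permits that reading but does not require it.

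**Shift in the contrast** = gap in weeks x assumed improvement per week.
- On time: from 0 to 2 x 0.03 = 0.06 SD, against PM+ (0.06 / 0.4 = 15% of the planned effect at most).
- 3-week slip: from 1 x 0.01 = 0.01 SD to 3 x 0.03 = 0.09 SD, in favour of PM+ (0.01 / 0.4 = 2.5%, about 3%; 0.09 / 0.4 = 22.5%, about 23%).

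**Where the sign changes.** The gap is zero when session 5 falls at week 6 (counting from session 5) or week 5 (counting from a post-assessment a week later). That corresponds to a slip of 1-2 weeks or 0-1 week respectively.

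**Scale.** At 133 per group the standard error of a simple difference is sqrt(2/133) = 0.12 SD, so even the largest shift above is below one standard error.

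**The case against.** The control arm is not without an anchor. Read together, the Procedure and Primary outcomes sections place CAU at about week 19, and on a strict weekly schedule the bracketed alternatives are close to equivalent. That stands, and it is why the on-time gap is only 0-2 weeks. But the CAU date has to be inferred from two sections, and it does not move when PM+ sessions do.

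A reader might infer that the design biases the result in favour of PM+. The documents do not support that. Delivered on time, PM+ is measured slightly earlier than CAU, which with natural improvement works against it. The direction reverses only once delay exceeds about 0-2 weeks, and the protocol gives no figure for delay or for natural recovery. Nor does a 3-week slip always produce a 3-week gap, because part of it is absorbed by the earlier starting position.

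A reader might also infer that no analysis could correct the problem. That is too strong. CAU is assessed at baseline, about week 6, about week 19 and 12 months, so a time trend can be estimated, and a model using actual time since randomization could adjust if the trend is smooth. The model in the Analysis section names no such term, though the statistical analysis plan, which is not shown, may. Such adjustment is a weaker remedy than a common schedule, because delay arises after randomization and in one arm only.

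Timing follow-up from the end of treatment is a defensible choice in itself, but it answers a different question and needs a defined counterpart in the control arm. Figure 1 and Table 1 are not shown and may set out a schedule, but they would not remove the difference between the two sections. Nor can a later analysis plan re-time visits that have already taken place.

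**Conclusion.** The point holds as a badly fixed anchor for the primary endpoint, not as a proven bias. Followed as written, the arms can be measured at different times since randomization for a reason that exists in one arm only. PM+ would be 0-2 weeks earlier than CAU if sessions run on time, and 1-3 weeks later under an assumed 3-week slip when its visit is timed from session 5 or from a post-assessment a week after it.

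At an assumed 0.01-0.03 SD per week, this means up to 0.06 SD against PM+ in the first case and 0.01-0.09 SD (3-23% of d = 0.4) in its favour in the second. The calendar arithmetic rests on the protocol, with 3 months read as 13 weeks. The conversion to SD rests wholly on the two assumptions. The point should be fixed because the repair is cheap and concerns the primary contrast, but it does not by itself threaten the trial's conclusions.

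**What to change.** Anchor both the post-assessment and the 3-month assessment to baseline or randomization in both arms, as the 12-month visit already is; for example, week 6, and week 6 plus 3 months. Use the same target date and the same window for every participant, regardless of how many sessions were attended or when session 5 took place. Word the Procedure and Primary outcomes sections identically.

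The cost is an edit to the text and a visit-scheduling rule; the sample size does not change. The one drawback is that PM+ participants whose sessions are delayed will be assessed somewhat less than 3 months after finishing.
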